#### 8.3.1. Serious Unexpected Drug Reactions

If there are serious, unexpected adverse drug reactions (SUSARs) associated with the use of the investigational product, ProKidney or its designee will notify the FDA and all participating Investigators on an expedited basis and in accordance with applicable regulations. It is the responsibility of the Investigator to promptly notify the IRB /EC and other appropriate institutional regulatory bodies of all unexpected serious adverse drug reactions involving risk to human subjects.

### 8.3.2. Pregnancy

Pregnancy is neither an AE nor an SAE, unless a complication relating to the pregnancy occurs. All reports of congenital abnormalities /birth defects are SAEs. Spontaneous miscarriages should be reported and handled as SAEs. However, elective abortions without complications should not be handled as AEs.

All pregnancies experienced by female subjects enrolled in this study are to be reported in the same time frame as SAEs using the Pregnancy Form of the CRF. The course of all pregnancies, including perinatal and neonatal outcome, regardless of whether the subject has discontinued participation in the study, will be followed until resolution, including follow-up of the health status of the newborn to 6 weeks of age.

The effects of administration of the investigational product on the pregnant female or the developing fetus are unknown. Therefore, female subjects of child-bearing potential who are planning a pregnancy during the course of the study, or who are not using a highly effective method(s) of birth control, or who are unwilling to continue using a highly effective method of birth control throughout the duration of the study are not eligible to participate in the study. (Refer to Exclusion Criterion # 23; [Section 5.2](#)).

### 8.4. Data Safety Monitoring Board

A Data Safety Monitoring Board (DSMB) will be chartered to oversee subject safety, especially as it relates to unexpected investigational product-related events. The DSMB will minimally consist of 3 members who have expertise directly related to protocol-specified activities. It will function independently, and its members will have no other engagement with ProKidney. The DSMB will meet by teleconference at regular intervals, depending on the speed of subject enrollment and the amount of new data generated. The DSMB will advise ProKidney on aspects concerning the safety of subjects participating in the clinical trial. Apart from reviewing study data, the DSMB will consider feedback from the Sponsor and Investigators. The DSMB will share its recommendations with the study centers, Institutional Review Boards /Ethics Committees, and regulatory authorities, as appropriate. Other specific activities and responsibilities of the DSMB will be detailed in the DSMB charter.

### 8.5. Dose Adjustment Criteria

The dates for the first 3 subjects who are scheduled to receive a second REACT injection under IND 16482 will be staggered at a minimum of 3-week intervals. The DSMB will sequentially review the status of each of these subjects prior to the next subject undergoing his/her second REACT injection. After the third subject has received his/her second REACT injection, the DSMB will meet to assess AEs and other safety parameters obtained to date for these 3 subjects described in the protocol. The DSMB may recommend changes concerning the second REACT injection as well as protocol-specified study evaluations, and/or follow-up procedures.

Apart from reviewing study data, the DSMB will evaluate relevant feedback from the Sponsor and Investigators.

### 8.6. Stopping Rules for an Individual Subject

The Investigator, Medical Monitor, DSMB, and Sponsor may remove any subject from the study for:

- Any clinical AE, laboratory abnormality, intercurrent illness, other medical condition or situation whereby continued participation in the study would not be in the best interest of the subject.
- Development of any exclusion criterion.

If a subject is terminated from the study, EOS assessments should be conducted at the last visit.

If any of the following events occur, no additional subjects can receive REACT injections until review by the DSMB has been completed:

- An SAE that is rated as severe or life-threatening and, in the judgment of the Investigator, is related to REACT or study procedures
- Death of an enrolled subject
- Similar SAE's in more than one subject that are related to REACT, in the judgment of the Investigator
- Inability to deliver a minimum of 50% of the dose of REACT in more than one subject due to surgical or other issues

## **8.7. Study Suspension or Study Termination**

As long as subjects are enrolled and participating in the study, including follow-up, the Medical Monitor, DSMB, IRB /EC, Sponsor, FDA and other regulatory agencies will review serious, unexpected, procedure- and product-related AEs.

Enrollment in the study will be suspended if any patient develops an apparent tumor, whether in the kidney or at a remote anatomic site. A DSMB review will then determine whether or not study amendment or termination is needed. The study will also be suspended in the event that two or more patients develop a similar unexpected SAE or AEs that are more severe than expected with the study drug or study procedures. A DSMB review will then determine whether or not study amendment or termination is needed. If a decision is made to suspend or terminate the study, the ProKidney will notify the Investigators /sites and ProKidney as well as the IRB /EC and regulatory authorities, as required.

The DSMB, IRB /EC, Sponsor, Investigator(s), FDA and other regulatory authorities, as part of their duties to ensure human subject protection, *may suspend the study at any time* due to concerns for the safety of study subjects. Once the clinical trial is halted (i.e., no new enrollments and no further REACT injections), a report will be submitted to the IRB /EC.

## 9. STATISTICAL METHODS AND PLANNED ANALYSES

### 9.1. Sample Size

Up to 10 subjects who complete screening procedures and satisfy all inclusion and exclusion criteria will be enrolled.

Statistical analyses will be primarily descriptive in nature and no statistical hypothesis testing is planned for the study. Unless otherwise specified, continuous variables will be summarized by presenting the number of non-missing observations (n), mean, standard deviation, median, minimum, and maximum. Categorical variables will be summarized by presenting frequency count and percentage for each category.

### 9.2. Criteria for Evaluation

#### 9.2.1. Analysis Objectives and Endpoints

##### 9.2.1.1. Primary

To assess the safety of REACT injected in one recipient kidney.

- ***Primary Endpoint:*** Procedure and/or product related AEs through 24 months post-injection.

##### 9.2.1.2. Secondary

To assess the safety and tolerability of REACT administration by assessing renal-specific AEs over a 24-month period following injection.

- ***Secondary Endpoints:*** Renal-specific laboratory assessments through 24 months post-injection.

##### 9.2.1.3. Exploratory

To assess the impact of REACT on renal function over a 24-month period following injection and on the Quality of Life.

- ***Exploratory Endpoints:*** 1) Clinical diagnostic and laboratory assessments of renal structure and function (including eGFR, serum creatinine, and proteinuria) to assess changes in the rate of progression of renal disease, 2) patient-reported outcomes from the Kidney Disease Quality of Life (KDQOL) and EQ-5D-5L surveys obtained at baseline (i.e., after randomization, but before REACT injection) through 24 months after the last REACT injection.

### 9.3. Demographic and Baseline Characteristics

Demographic data and baseline characteristics will be summarized via sample size, mean, standard deviation, median, minimum, and maximum for the continuous variables as well as the frequency and proportion for categorical variables. These summaries will be produced for both the full analysis set and the injection analysis set. Demographic and baseline characteristic information will be presented as descriptive statistics; generating inferential statistics is not planned. These data will be provided in a tabular listing.

## 9.4. Efficacy Analysis

The primary efficacy endpoint is serial measurements of eGFR obtained at 1, 3, 6, 12, 15, 18, 21, and 24 months after the last REACT injection. GFR will be estimated using the Chronic Kidney Disease Epidemiology Collaboration (CKD-EPI) equation that incorporates both serum creatinine and Cystatin C.

Estimated GFR measured at each time point will be summarized by presenting descriptive statistics of raw data and change from baseline values for each treatment group.

## 9.5. Exploratory Analysis

An exploratory analysis will be conducted to examine potential changes in health-related Quality of Life (HR-QoL).

## 9.6. Statistical Methods

Subjects will complete the KDQOL-SFTTM survey (i.e., Kidney Disease and Quality of Life Short Form). The KDQOL-SF is a 36-item, validated, HR-QoL instrument relevant to patients with kidney disease. This disease-specific, HR-QoL instrument consists of the following subscales:

- The “SF-12 measure of physical (PCS) and mental (MCS) functioning” contains items about general health, activity limits, ability to accomplish desired tasks, depression and anxiety, energy level, and social activities.
- The “Burden of Kidney Disease subscale” contains items about how kidney disease interferes with daily life, takes up time, causes frustration, or makes the respondent feel like a burden.
- The “Symptoms and Problems subscale” contains items about how bothered a respondent feels by sore muscles, chest pain, cramps, itchy or dry skin, shortness of breath, faintness/dizziness, lack of appetite, feeling washed out or drained, numbness in the hands or feet, nausea, or problems with dialysis access.
- The “Effects of Kidney Disease on Daily Life subscale” contains items about how bothered the respondent feels by fluid limits, diet restrictions, ability to work around the house or travel, feeling dependent on doctors and other medical staff, stress or worries, sex life, and personal appearance.

## 9.7. Safety Analysis

### 9.7.1. Laboratory Evaluations

Baseline values will be collected immediately prior to REACT injection. Observed and change from baseline laboratory data will be summarized via sample size, mean, standard deviation, median, minimum, and maximum for the continuous variables as well as frequency and proportion for the categorical variables. Laboratory abnormalities will be defined using the NCI CTCAE grading scheme. Abnormal laboratory values will be flagged as above or below the normal range. The results of laboratory testing for renal function, specifically sCr, BUN, and urinary albumin, are of particular interest for this study.

The incidence of treatment-emergent laboratory abnormalities, defined as values that increase at least one toxicity grade between baseline and any time post-baseline up to six months following REACT injection, will be summarized. If baseline data are missing, then the latest value between

biopsy and injection will be used as the baseline value. If baseline and pre-injection data are missing, then any graded abnormality (i.e., at least a Grade 1) will be considered as treatment-emergent. These values will be summarized for both the full analysis set and the injection analysis set. Observed and change from baseline values will be presented as descriptive statistics; generating inferential statistics is not planned. These data will be provided in a tabular listing.

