#### 1.1.2. Progressive Staging of CKD

The major causes of CKD are diabetes and hypertension. Nearly half of all CKD cases arise from diabetes with or without hypertension. The incidence of CKD continues to increase, primarily due to the increased incidence of Type 2 Diabetes Mellitus (T2DM).

Staging and grading of kidney function is most often quantified by the estimated glomerular filtration rate (GFR), which is defined as “the volume of plasma from which a given substance is completely cleared by glomerular filtration per unit time”. Creatinine clearance is the principal endogenous marker that is used to measure GFR. In February 2002, with the aim of providing a uniform definition of CKD, the Kidney Disease Outcomes Quality Initiative of the US Kidney Foundation defined CKD and the various stages of CKD (Table 4). For example, the threshold for CKD is 60 mL/min/1.73m^2, which is less than one-half of the GFR for a normal, young adult male (120-130 mL/min/1.73m^2). Additionally, there is a heightened risk for CKD complications when the GFR is 60 mL/min/1.73m^2 and lower.

Table 4 defines CKD stages according to GFR measurements, and the relative prevalence and clinical action taken at each stage. The initial stage of diabetic nephropathy (Stage 1) occurs over a period of several years and is characterized by microalbuminuria (30-300 mg/24 hr.) followed by macroalbuminuria (> 300 mg/24 hr.). As the ability of the kidney to filter blood waste products declines, serum creatinine rises. With increasing kidney damage (Stages 2-4), rising blood pressure further exacerbates kidney disease. When the kidneys cease to function entirely (Stage 5 [ESRD]), renal replacement therapy (dialysis or transplantation) is required.

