2.2.3 Exploratory Endpoints

Exploratory endpoints include:

- 1) Clinical diagnostic and laboratory assessments of renal structure and function (including eGFR, serum creatinine, and proteinuria) to assess changes in the rate of progression of renal disease.

- a. Clinical diagnostic assessments of renal structure and function consist of results from renal ultrasounds (cortical thickness, length, and volume by treated/untreated kidney) and renal scintigraphy (differential renal function by treated/untreated kidney).
- b. Laboratory assessments considered exploratory endpoints include: eGFR as estimated by three Chronic Kidney Disease Epidemiology Collaboration (CKD-EPI) equations [2009 CKD-EPI serum creatinine equation, 2012 CKD-EPI cystatin C equation, and 2012 CKD-EPI serum creatinine-cystatin C equation], serum creatinine, 24 hour urine albumin, and 24 hour urine protein.

2) Patient-reported outcomes from Kidney Disease Quality of Life (KDQOL) and EQ-5D-5L surveys obtained at baseline (i.e., before REACT injection) through 24 months after the last REACT injection.

3) Time to dialysis

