4. GENERAL CONSIDERATIONS FOR DATA ANALYSIS

Unless otherwise specified, continuous variables will be summarized by presenting the number of non-missing observations (n), mean, standard deviation, median, 25th percentile, 75th percentile, minimum, and maximum. Categorical variables will be summarized by presenting frequency count and percentage for each category. All tabulations will be based on pooled data across centers. For the summary statistics of all numerical variables unless otherwise specified, minimum and maximum will be displayed to the same level of precision as reported. Mean, median, 25% and 75% quartiles will be displayed to one level of precision greater than the data collected. Standard deviation will be displayed to two levels of precision greater than the data collected.

CTI Clinical Trial and Consulting Services will perform all efficacy and safety statistical analyses using SAS for Windows statistical software, version 9.4 or higher (SAS, Cary, NC), except where other software may be deemed more appropriate.

Subject data will be listed, sorted by subject number.

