6.2 Secondary Efficacy Endpoints and Analyses

The secondary efficacy endpoints are renal-specific laboratory assessments including: eGFR as estimated by three CKD-EPI equations [2009 CKD-EPI serum creatinine equation, 2012 CKD-EPI cystatin C equation, and 2012 CKD-EPI serum creatinine-cystatin C equation], random urine albumin to creatinine ratio (UACR), 24 hour urine albumin, 24 hour urine protein, cystatin C, serum creatinine, blood urea nitrogen, bicarbonate, potassium, phosphorus, calcium, intact parathyroid hormone (iPTH), hemoglobin, and hematocrit.

Measurements taken after dialysis has started will be removed from all efficacy analyses.

Listings of lab assessments will include a notation for assessments taken after the start of dialysis so that it is clear which records are included in the efficacy analyses.

Renal-specific lab values will be summarized by presenting descriptive statistics of raw data and change from baseline values at each time point using the IAS.

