6.3.4 Rate of Progression of Renal Disease

Using the IAS, the rate of progression of renal disease will be assessed graphically for eGFR as estimated by the 2009 CKD-EPI serum creatinine equation, serum creatinine, and 24 hour urine albumin, and 24 hour urine protein. For each subject a plot of the lab result versus time (in study days) will be displayed, showing vertical lines at biopsy date, 1st and 2nd injection, and the initiation of dialysis, if it is administered. Additionally, for eGFR, the rate of progression of renal disease will be assessed by estimating the annualized eGFR slope over time for each subject. Each subject will serve as his or her own control. The subject's previous medical history, which must include a minimum of 6 months of observation of renal function, will serve as the control for rate of progression of renal insufficiency. The historical eGFR measurements as well as all on study measurements taken prior to the first REACT injection will constitute the pre-injection period for this analysis.

The annualized rate of eGFR decline for the pre-injection, post-second injection, and post-injection periods will be estimated separately by linear mixed effects models. That is, separate models will be fit for each of the specific time periods: pre-injection, post-second injection, and post-injection periods. Each subject with a minimum of 3 observations during the period of interest will be modeled. The model will include unscheduled visits, and only the last measurement if there was a re-test on the same day.

For the pre-injection period, the linear mixed effects model will include eGFR as the dependent variable, and time (in years, derived as study day/365) as the independent variable. To account for between-subject variability in eGFR trajectories, random slopes and intercepts will be included. An unstructured covariance matrix will be used for the model. If the model cannot be fit with the unstructured covariance matrix, the following structure will be tried in the order listed below (decreasing number of parameters) until the one of them fit the model:

1. First-order autoregressive moving average (ARMA(1,1))
2. First-order autoregressive (AR(1))
3. Compound symmetry (CS)
4. Variance Components (VC)

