7.3 Clinical Laboratory Assessments

Measurement of clinical laboratory parameters will be conducted at the time points presented in the [Appendix B](#). For purposes of analyses, laboratory results based upon standardized units will be used.

Results from all clinical laboratory parameters including pregnancy test will be presented in data

listings for the FAS.

For the IAS, a summary of the laboratory parameters at baseline, each scheduled post-baseline visit and change from baseline will be provided by test category (e.g., chemistry, hematology, etc.). Continuous clinical laboratory values will be summarized by presenting descriptive statistics. UACR will be considered as a categorical variable with three categories: <30 mg/g, 30 – 299 mg/g, and \geq 300mg/g. Qualitative results at each time point measured will be summarized by presenting the number and percentage of subjects.

Laboratory assessment results from unscheduled visits will be excluded from table summaries but will be included in data listings. When there are repeat measurements for a given visit (i.e. retests), only the last measurement will be listed and used in the table summaries.

Results that are reported as above or below the limit of quantitation (e.g. <4, >10) will be not be imputed and will be treated as missing values for summarization purposes. The originally reported result (e.g. <4, >10) will be displayed in the listings.

Laboratory abnormalities will be defined using the NCI CTCAE grading scheme. Abnormal laboratory values will be flagged as above or below the normal range.

For the IAS, the incidence of treatment-emergent laboratory abnormalities, defined as values that increase at least one toxicity grade between baseline and post-baseline up to six months following REACT injection, will be summarized. If baseline and pre-injection data are missing, then any graded abnormality (i.e., at least a Grade 1) will be considered as treatment-emergent. These values will be summarized descriptively for the IAS.

Additionally, for the IAS, shift tables (shift from baseline to the worst post-baseline value) will be presented split by the inter-injection, post-second injection period, and the post-injection period as described in [section 4.9](#). Shift tables will describe the shift in CTCAE grades when available, or the shift from low/normal/high when CTCAE grades are not available.

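### No proportional (log-scale) summary is planned for UACR, 24-hour urine albumin or 24-hour urine protein, so the mean and SD of absolute change mainly reflect the heaviest excretors

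*Protocol*

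**What the plan says.** Protocol 9.7.1 gives one recipe for all continuous laboratory tests: "Observed and change from baseline laboratory data will be summarized via sample size, mean, standard deviation, median, minimum, and maximum". The same section says that results for renal function, "specifically sCr, BUN, and urinary albumin, are of particular interest for this study".

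SAP 6.2 lists UACR, 24-hour urine albumin and 24-hour urine protein among the secondary efficacy endpoints, next to potassium and calcium, and says: "Renal-specific lab values will be summarized by presenting descriptive statistics of raw data and change from baseline values at each time point". The default statistics in SAP 4 are n plus "mean, standard deviation, median, 25th percentile, 75th percentile, minimum, and maximum". The two 24-hour measures are also exploratory endpoints in SAP 2.2.3 ("serum creatinine, 24 hour urine albumin, and 24 hour urine protein"), intended to assess change in the rate of progression.

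Two further displays matter. SAP 6.3.4 assesses progression graphically for 24-hour albumin and protein: "For each subject a plot of the lab result versus time (in study days) will be displayed". SAP 7.3 says that "UACR will be considered as a categorical variable with three categories", the highest being 300 mg/g and above with no upper limit.

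Neither document mentions a log transformation, geometric mean, ratio to baseline or percent change for any urinary measure. Enrolment is capped at 10, missing values are not imputed (SAP 4.5), and values after the start of dialysis are removed (SAP 6.2). No inclusion or exclusion criterion limits albuminuria or proteinuria.

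**The concern.** Urinary albumin and protein excretion can differ between patients by large factors, and response is naturally read as a proportion. The same 30% fall is a small number of milligrams in a light excretor and a large one in a heavy excretor. A mean of absolute changes weights each subject's proportional change by that subject's baseline. Its SD mixes variation in response with variation in starting level.

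In a descriptive study the summary tables are the output. If the mean change in 24-hour albumin is read as the group's response, one or two heavy excretors can set its size and sometimes its sign. Nothing else in the plan gives a group figure for proportional change.

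**Working it through.** There is no planned figure to reproduce: the plan states no effect size, SD or power.

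**Structure.** Let Bᵢ be subject i's baseline and rᵢ the ratio of follow-up to baseline.

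- Absolute change: Dᵢ = Bᵢ(rᵢ − 1).
- Mean change divided by mean baseline: ΣBᵢ(rᵢ − 1) / ΣBᵢ, an average of proportional changes weighted by baseline.
- Geometric mean ratio (GMR): exp{(1/n) Σ ln rᵢ}, with equal weight per subject.

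If every rᵢ is the same and below 1, every Dᵢ is negative, so a uniform proportional fall cannot appear as a rise. Reversal needs responses that vary between subjects.

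**Worked example.** Assumed baselines in mg/24 h: 50, 100, 200, 300, 500, 800, 1,200, 2,000, 3,000 and 6,000 (sum 14,150). This is a deliberately wide spread: 6,000/50 = 120-fold.

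- All ten fall 30%: mean change = −0.3 × 1,415 = −424.5. The heaviest subject supplies 1,800/4,245 = 42% of the total, and the top two 2,700/4,245 = 64%.
- Nine fall 30% and the heaviest rises 40%: total = −0.3 × 8,150 + 2,400 = −45, so the mean is −4.5 (SD 891). The median is −120, the quartiles by linear interpolation are −330 and −37.5, and the GMR is (0.7⁹ × 1.4)^(1/10) = 0.75.
- Break-even: 0.3 × 8,150/6,000 = 40.75%. If the heaviest rises 50%, the mean is (3,000 − 2,445)/10 = +55.5, an apparent rise. The median stays at −120 and the GMR is 0.76.

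**Simulation.** Inputs from the documents: n = 10, and absolute change as the planned scale. Assumed inputs: log-normal baseline with log-SD 0.7, 1.0 or 1.3; log-normal ratio, independent of baseline, with true GMR 0.7 and within-subject log-SD s of 0.3, 0.4 or 0.6. Each setting had 200,000 trials. Ranges are over the baseline log-SDs.

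| s | Mean change shows a rise | Median change shows a rise | GMR shows a rise | True arithmetic ratio, 0.7 × exp(s²/2) |
|---|---|---|---|---|
| 0.3 | 0.5-2% | 0.1% | <0.1% | 0.73 |
| 0.4 | 3.5-7% | about 1% | 0.2% | 0.76 |
| 0.6 | 19-22% | 6-6.5% | 3% | 0.84 |

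In a typical (median) trial the largest single subject supplies about 28-40% of the summed absolute change.

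A separate grid (baseline log-SD 0.5-1.5, same true ratio) shows the effect of fewer subjects. At s = 0.5 the mean shows a rise in 8.8-15.1% of trials with n = 10 and in 11.8-16.8% with n = 7.

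**The case against.** The plan does not rest on the mean and SD. It reports the median, quartiles and range, lists every laboratory result by subject, and puts UACR into categories. For 24-hour albumin and protein, progression is assessed through one plot per subject, where no subject can influence another's curve. With at most 10 subjects listed, a reader can work out the ratios. No hypothesis test is planned and no decision uses the mean. All of this stands, and it limits the consequence.

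Three further points also stand.

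- **Estimand.** The arithmetic mean answers a different question. If mean excretion rises in the sample, total excretion did rise. Part of the reversal at s = 0.6 arises because the true fall in the arithmetic mean is 16%, not 30%. It is still a fall in every setting tabulated, so a rise is wrong in sign on either scale.
- **Spread.** Protocol 1.1.2 gives albumin bands that are ten-fold wide and open at the top, but places them in the initial stage of diabetic nephropathy. They do not show the spread in a cohort entering at eGFR 14-20, so the baseline log-SDs remain assumptions.
- **Precision.** A reader might infer that the plan wastes statistical precision, by comparing confidence intervals on the two scales. No interval or test is planned for these summaries, so that comparison has no bearing on the plan.

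What the objection does not supply is a group summary of proportional change. The median and quartiles of absolute change are still in milligrams, plots and listings give no group figure, and the UACR categories cannot show a fall that stays at or above 300 mg/g.

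**Conclusion.** The point holds as a cheap improvement to a descriptive plan. No proportional summary is planned for three urinary measures, two of which are also exploratory endpoints for progression. The mean and SD of absolute change will largely describe the heaviest excretors.

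The chance of a misleading sign depends on how variable the responses are: about 2% or less at within-subject log-SD 0.3, and about one in five at 0.6, if the true ratio is 0.7. These figures assume log-normal values and ratios independent of baseline; the documents supply no albumin or protein data to check them.

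A reader might go further and infer that heavy excretors dominate the whole result, or that any real proportional fall may appear as a rise. The documents do not support this. The planned median moves far less, the per-subject displays are unaffected, and a uniform fall cannot reverse.

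**What to change.** In SAP 6.2 and 7.3, for UACR, 24-hour urine albumin and 24-hour urine protein, add the geometric mean at each visit and the geometric mean ratio to baseline, shown as percent change, with its log-scale SD. Keep the raw median, quartiles and range. In SAP 6.3.4, plot 24-hour albumin and protein on a log axis. At the same time, state whether UACR is summarised as continuous (SAP 6.2), categorical (SAP 7.3) or both, since the two sections now differ.

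The cost is a few lines of SAP text and programming, with no new data or visits. One rule has to be added: how zero or below-quantification values enter the log scale. SAP 7.3 now treats results outside the quantification limits as missing for summaries, so the rule should be fixed before the final analysis.
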